### 3.3 Registration – Inclusion Criteria

- 3.31 Histologic confirmation of Stage III melanoma, as defined by the American Joint Committee on Cancer, 8th revised edition.
- 3.32 Arms A and B only: Documentation of BRAFV600 mutation status in melanoma tumor tissue (archival or newly obtained) through use of a CLIA-approved clinical mutation test.
- 3.33 Surgically resectable disease, as determined by a melanoma surgical oncologist.
- 3.34 Eastern Cooperative Oncology Group (ECOG) Performance Status of 0 or 1 (See [Appendix I](#)).
- 3.35 Life expectancy  $\geq 26$  weeks.
- 3.36 The following laboratory values obtained  $\leq 14$  days prior to registration:
  - Absolute neutrophil count (ANC)  $\geq 1500/\text{mm}^3$
  - Platelet count  $\geq 100,000/\text{mm}^3$
  - Hemoglobin  $\geq 9.0$  g/dL
  - Direct bilirubin  $\leq$  institutional upper limit of normal (ULN)
  - Aspartate transaminase (AST) and alanine transaminase (ALT)  $\leq 2 \times$  ULN
  - Alkaline phosphatase  $< 2.5 \times$  ULN
  - Creatinine  $\leq 1.5 \times$  ULN or creatinine clearance (CrCl)  $\geq 45$  mL/min on the basis of measured CrCl from a 24-hour urine collection or Cockcroft-Gault glomerular filtration rate estimation:  

$$\text{CrCl} = \frac{(140 - \text{age}) \times (\text{weight in kg})}{72 \times (\text{serum creatinine in mg/dL})} \quad (\times 0.85 \text{ if female})$$
- 3.37 Arms A and B only: LVEF  $\geq 50\%$  or institutional LLN  $\leq 6$  months prior to registration.
- 3.38 Arms A and B only: Average QTc  $\leq 450$  ms on triplicate 12 lead ECG  $\leq 28$  days prior to registration.  
NOTE: QTc intervals will be corrected using Fridericia's formula (Fridericia 1920)
- 3.39a Negative pregnancy test done  $\leq 7$  days prior to registration, for persons of childbearing potential only.
- 3.39b For persons of childbearing potential: agreement to remain abstinent (refrain from heterosexual intercourse) or use a contraceptive method with a failure rate of  $< 1\%$  per year during the treatment period and for 6 months after the last dose of study treatment.
- 3.39c For persons able to father a child: agreement to remain abstinent (refrain from heterosexual intercourse with a person of childbearing potential) or use contraceptive measures, and agreement to refrain from donating sperm during the treatment period and for 6 months after the last dose of study treatment.
- 3.39d Provide written informed consent.

- 3.39e Willing to return to enrolling institution for follow-up (during the Active Monitoring Phase of the study).
- 3.39f Willing to provide tissue, blood, and stool samples for correlative research purposes (see Sections 6.22, 14.1 and 17.1).
- 3.39g Arm C Only: Negative serology for acute Epstein-Barr virus (EBV) infection (negative EBV VCA IgM).
- 3.4 Registration – Exclusion Criteria
- 3.41 Received anticancer treatments or investigational agents during pre-registration period.
- 3.42 Clinically suspected non-nodal metastatic melanoma
- 3.43 Arm A only: For BRAF-mutant patients only: Anticipated use of any concomitant medication  $\leq 7$  days prior to registration that is known to cause QT prolongation (which may lead to torsade de pointes).
- 3.44 Arms A and B only: History of malabsorption or other clinically significant metabolic dysfunction that may interfere with absorption of oral study treatment or inability or unwillingness to swallow oral medication.
- 3.45 Signs or symptoms of infection or has received antibiotics  $\leq 14$  days prior to registration.  
NOTE Patients receiving prophylactic antibiotics (e.g., to prevent a urinary tract infection or chronic obstructive pulmonary disease exacerbation) are eligible for the study.
- 3.46 Any of the following because this study involves investigational agents whose genotoxic, mutagenic, and teratogenic effects on the developing fetus and newborn are unknown:
- Pregnant persons
  - Nursing persons
  - Persons of childbearing potential who are unwilling to employ adequate contraception
- 3.47 Treatment with a live, attenuated vaccine  $\leq 4$  weeks prior to registration, or anticipation of need for such a vaccine during the course of the study
- 3.48 Treatment with systemic immunosuppressive medication (including, but not limited to, prednisone, cyclophosphamide, azathioprine, methotrexate, thalidomide, and anti-tumor necrosis factor (TNF) - $\alpha$  agents)  $\leq 2$  weeks prior to registration, or anticipation of need for systemic immunosuppressive medication during the course of the study  
NOTE: Patients who have received acute, low-dose systemic steroids ( $\leq 10$  mg/day oral prednisone or equivalent) prior to registration or a one-time pulse dose of systemic immunosuppressant medication (e.g., 48 hours of corticosteroids for a contrast allergy) are eligible for the study.  
NOTE: The use of inhaled corticosteroids for chronic obstructive pulmonary disease or asthma, mineralocorticoids (e.g., fludrocortisone), or low-dose corticosteroids for patients with orthostatic hypotension or adrenocortical insufficiency is allowed.
- 3.49a Requirement for concomitant therapy or food that is prohibited during the study, as described in [Appendix III](#).

- 3.49b Arms A and B only: Inability to abstain from alcohol during neoadjuvant phase.
- 3.49c Arm C only: Known Epstein-Barr virus (EBV) infection.  
NOTE: Patients with symptoms such as splenomegaly, fever, sore throat, non-malignant cervical lymphadenopathy, and/or tonsillar exudate, should undergo an EBV polymerase chain reaction (PCR) test to screen for *acute* infection or suspected chronic active infection. Patients with a positive EBV PCR test are excluded.

#### 4.0 Study Schedules

##### 4.1 Test Schedule for Arms A and B

Tests and procedures			Active Monitoring Phase								Observation 
				Neoadjuvant treatment			Surgical Period		Adjuvant Treatment		
	Pre-registration period	≤14 days prior to registration	After registration prior to start of treatment on C1D1	D15 of each Neoadj Treatment Cycle	D8, D22 of each Neoadj Treatment Cycle	At completion of each Neoadj Treatment Cycle	After completion of ALL Neoadj Tx (prior to surgery)	At time of Surgery	≤7 days prior to start of Adjuvant Treatment	At completion of each Adjuvant Treatment Cycle: D21	
Window				±3 days	±3 days	±3 days	±3 days			±3 days	±14 days
History and exam, Wt, PS 	X			X		X			X	X	X
Height	X										
Adverse event assessment		X		X		X			X	X	X
Evaluation of lymphedema using NCI CTCAE v5.0 										X	X
Pregnancy test 		X									
Hematology group: CBC with differential		X		X		X			X	X	X
Chemistry group: AST, ALT, alkaline phosphatase, total and direct bilirubin, creatinine, random glucose		X		X	X R5	X			X	X	X
Neoadjuvant treatment period only: albumin, BUN, calcium, potassium, phosphorus, sodium, GGT		X		X		X					

 Observation every 3 months for max of 3 years post-surgery or until disease recurrence (only for patients who undergo surgery)

 Exam includes monitoring for non-cutaneous SCC of head and neck consisting of at least a visual inspection of oral mucosa and lymph node palpation, and dermatologic conditions

 At completion of adjuvant treatment and 12 months post surgery only; Please put results on Adverse Event: Other CRF

 For persons of childbearing potential only: Must be done ≤7 days prior to registration.

 LFTs only (AST, ALT, AlkPhos, tbili, dbili); for visits when patient does not need to be at treating institutions (Mayo Clinic or UMN), LFTs may be done locally and sent to treating institutions

Tests and procedures			Active Monitoring Phase								Observation 
				Neoadjuvant treatment			Surgical Period		Adjuvant Treatment		
	Pre-registration period	≤14 days prior to registration	After registration prior to start of treatment on C1D1	D15 of each Neoadj Treatment Cycle	D8, D22 of each Neoadj Treatment Cycle	At completion of each Neoadj Treatment Cycle	After completion of ALL Neoadj Tx (prior to surgery)	At time of Surgery	≤7 days prior to start of Adjuvant Treatment	At completion of each Adjuvant Treatment Cycle: D21	
Window				±3 days	±3 days	±3 days	±3 days			±3 days	±14 days
INR 	X						X				
AM Cortisol							X				
TSH (reflex per institutional std)		X				X			X	X 	X
Echocardiogram or MUGA scan (LVEF)		X 				X 					
ECG  and CPK		X		X 		X					
Ophthalmic exam 	X R			X R							
Clinical staging	X 										
Pathologic staging								X			
Imaging: PET/CT (preferred), or CT and/or MRI imaging of chest, abdomen, and pelvis	X 						X			X 	X
Biopsy for BRAF testing (or archival biopsy specimen) R	X										

 Only for patients receiving therapeutic anticoagulation: stable anticoagulant regimen and stable INR

 Thyroid testing once per cycle or as clinically indicated

 Baseline echocardiogram or MUGA scan obtained ≤6 months prior to registration.

 Repeat echo at one month after starting treatment and prior to surgery. All patients restarting treatment with a dose reduction of cobimetinib because of a decrease in LVEF should have LVEF measurements taken after approximately 2 weeks and 4 weeks or until LVEF recovers to LLN or 50%.

 Triplicate 12-lead ECG recordings will be obtained at screening. Single 12-lead ECG recordings will be obtained prior to and 2-4 hours after the morning doses of cobimetinib and vemurafenib for all neoadjuvant treatment cycles: Day 15. QTc intervals will be corrected using Fridericia's formula (Fridericia 1920).

 Repeat ECG and CPK at ~14 days after initiating neoadjuvant therapy and monthly for 3 months.

 Required at baseline, and after completion of first cycle of neoadjuvant treatment, then as clinically indicated based on AE assessment

 Submit clinical note or imaging documenting recurrent nodal metastasis, clinically detectable nodal metastasis, or metastatic involvement of more than one nodal basin

 ≤30 days prior to registration

 Completion of 4th and 8th cycle of adjuvant treatment only

Tests and procedures			Active Monitoring Phase								Observation 
				Neoadjuvant treatment			Surgical Period		Adjuvant Treatment		
	Pre-registration period	≤14 days prior to registration	After registration prior to start of treatment on C1D1	D15 of each Neoadj Treatment Cycle	D8, D22 of each Neoadj Treatment Cycle	At completion of each Neoadj Treatment Cycle	After completion of ALL Neoadj Tx (prior to surgery)	At time of Surgery	≤7 days prior to start of Adjuvant Treatment	At completion of each Adjuvant Treatment Cycle: D21	
Window				±3 days	±3 days	±3 days	±3 days			±3 days	±14 days
Research blood specimens (see Section 14.0) 16,R			X 			X	X 		X	X 	X
Research stool specimen, buccal (cheek) and skin swabs 			X				X	X 		X 	X 
Research tissue specimens (see Section 17.0) 24R			X 					X 			X 
Medication diary 						X	X				

Neoadjuvant treatment cycles = 28 ±3 days (maximum of 3 cycles)

Adjuvant treatment cycles = 21 ±3 days (maximum of 8 cycles)

R= Research funded

 Blood specimens will be collected and submitted per Section 14.0

 Research blood specimens will be collected and submitted per Section 14.0. Samples may be collected prior to registration using the pre-registration number. If the patient is not registered, the samples will be destroyed.

 Collect at end of all neoadjuvant treatment prior to surgery (NOTE: Different from end of cycle collection – see Section 14.0)

 At completion of 4th and 8th cycle of adjuvant treatment only

 Microbiome specimens may be collected and processed during pre-registration period. If the patient does not register onto this study, these specimens will be destroyed. Following registration, microbiome specimens are collected and are to be submitted per Section 14.0.

 Skin swab collected during surgery.

 Microbiome stool collection at end of adjuvant therapy (≤2 weeks after last dose of study drug)

 Microbiome stool specimen at first recurrence (optional) to be collected and submitted per Section 14.0.

 Tissue specimens must be collected and submitted per Section 17.0

 Research tissue specimens may be collected at the same time as that needed for BRAF testing. Research tissue specimens should be processed as outlined in Section 17.0.

Following registration, research tissue samples should be shipped per Section 17.0. Specimens from patients who do not register onto the study should be destroyed or keep at harvesting site according to local policies.

 Surgical research tissue specimens should be shipped per Section 17.0.

 Tissue biopsy specimen at first recurrence (optional) to be collected and submitted per Section 17.0

 The diary must begin the day the patient starts taking the medication and must be completed per protocol and returned to the treating institution OR compliance must be documented in the medical record by any member of the care team

## 4.2 Test Schedule for Arm C

Tests and procedures	Prior to Registration		Active Monitoring Phase						Observation 
				Neoadjuvant treatment	Surgical Period		Adjuvant Treatment		
	Pre-registration period	≤14 days prior to registration	After registration prior to start of treatment on C1D1	At completion of each Neoadj Treatment Cycle	After completion of ALL Neoadj Tx (prior to surgery)	At time of Surgery	≤7 days prior to start of Adjuvant Treatment	At completion of each Adjuvant Treatment Cycle	
Window				±3 days	±3 days			±3 days	±14 days
History and exam, Wt, PS	X			X			X	X	X
Height	X								
Adverse event assessment		X		X			X	X	X
Evaluation of kymphedema using NCI CTCAE v5.0 								X	X
Pregnancy test 		X							
Hematology group: CBC with differential		X		X			X	X	X
Chemistry group 		X		X			X	X	X
Neoadjuvant treatment period only: potassium, sodium		X		X					
INR 	X				X				
AM Cortisol					X				
TSH (reflex per institutional std)		X		X			X	X 	X
EBV testing		X 							
ECG 		X							
Clinical staging	X 								
Pathologic staging						X			

 Observation (clinical follow-up) every 3 months for max of 3 years post-surgery or until disease recurrence (only for patients who undergo surgery)

 At completion of adjuvant treatment and 12 months post surgery only; Please put results on Adverse Event: Other CRF

 For persons of childbearing potential only: Must be done ≤7 days prior to registration.

 AST, ALT, alkaline phosphatase, total & direct bilirubin, creatinine, random glucose

 Only for patients receiving therapeutic anticoagulation: stable anticoagulant regimen and stable INR

 Thyroid testing once per cycle or as clinically indicated

 EBV serology: Should include EBV VCA IgM. If IgM result is positive, patient is not eligible.

 Needed at baseline, thereafter as clinically indicated

 Submit clinical note or imaging documenting recurrent nodal metastasis, clinically detectable nodal metastasis, or metastatic involvement of more than one nodal basin

Tests and procedures	Prior to Registration		Active Monitoring Phase						Observation 
				Neoadjuvant treatment	Surgical Period		Adjuvant Treatment		
	Pre-registration period	≤14 days prior to registration	After registration prior to start of treatment on C1D1	At completion of each Neoadj Treatment Cycle	After completion of ALL Neoadj Tx (prior to surgery)	At time of Surgery	≤7 days prior to start of Adjuvant Treatment	At completion of each Adjuvant Treatment Cycle	
Window				±3 days	±3 days			±3 days	±14 days
Imaging per clinical standards 	X 				X			X 	X
Biopsy for BRAF testing (or archival biopsy specimen) and clip placement R	X								
Research blood specimens (see Section 14.0) 41,R			X 	X	X 		X	X 	X
Research stool specimen, buccal (cheek) and skin swabs 			X		X	X 		X 	X 
Research tissue specimens (see Section 17.0) 49R			X 			X 			X 

Neoadjuvant treatment cycles = 21 ±3 days (maximum of 4 cycles); Adjuvant treatment cycles = 21 ±3 days (maximum of 8 cycles); R= Research funded

 Current Mayo Clinic standard: PET/CT (preferred), or CT and/or MRI imaging of chest, abdomen, and pelvis

 ≤30 days prior to registration

 Completion of 4th and 8th cycle of adjuvant treatment only

 Blood specimens will be collected and submitted per Section 14.0

 Research blood specimens will be collected and submitted per Section 14.0. Samples may be collected prior to registration using the pre-registration number. If the patient is not registered, the samples will be destroyed.

 Collect at end of all neoadjuvant treatment prior to surgery (NOTE: Different from end of cycle collection – see Section 14.0)

 At completion of 4th and 8th cycle of adjuvant treatment only

 Microbiome specimens may be collected and processed during pre-registration period. If the patient does not register onto this study, these specimens will be destroyed.

Following registration, microbiome specimens are collected and are to be submitted per Section 14.0.

 Skin swab collected during surgery.

 Microbiome stool collection at end of adjuvant therapy (≤2 weeks after last dose of study drug)

 Microbiome stool specimen at first recurrence (optional) to be collected and submitted per Section 14.0.

 Tissue specimens must be collected and submitted per Section 17.0

 Research tissue specimens may be collected at the same time as tissue collection for BRAF testing. Research tissue specimens should be processed as outlined in Section 17.0. Following registration, research tissue samples should be shipped per Section 17.0. Specimens from patients who do not register onto the study should be destroyed or kept at harvesting site according to local policies.

 Surgical research tissue specimens should be shipped per Section 17.0.

 Tissue biopsy specimen at first recurrence (optional) to be collected and submitted per Section 17.0

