### 3.0 Patient Eligibility

#### 3.1 Pre-Registration – Inclusion Criteria

3.11 Age  $\geq 18$  years.

3.12 High-risk stage III melanoma, defined as (any of the following):

- recurrent nodal metastasis, or
- clinically detectable nodal metastasis, or
- metastatic involvement of more than one nodal basin

NOTE: For the purpose of pre-registration, high-risk stage III melanoma is defined based on clinical and imaging assessment (PET/CT, CT, or MRI). Histologic confirmation of nodal metastatic disease is not needed at the time of pre-registration, provided there is histologic confirmation of primary melanoma or a prior lymph node metastasis.

3.13 Willing to submit archival tissue from a lymph node biopsy or undergo a needle biopsy (with clip placement) for BRAF testing and for research purposes.

3.14 Willing to forego anticancer treatments or investigational agents during pre-registration period.

3.15 The following laboratory values obtained  $\leq 28$  days prior to pre-registration:

- Only for patients receiving therapeutic anticoagulation: stable anticoagulant regimen and stable INR

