#### 3.2 Pre-Registration – Exclusion Criteria

3.21 Prior systemic anti-cancer therapy for melanoma (e.g., chemotherapy, hormonal therapy, targeted therapy, immunotherapy including anti-PD-1, anti-PDL1 agents, or other biologic therapies), with the following exceptions: adjuvant treatment with interferon, IL-2, GM-CSF or vaccine therapies are allowed, if discontinued  $\geq 28$  days prior to pre-registration.

3.22 Receiving any other investigational agent which would be considered as a treatment for the primary neoplasm.

3.23 For patients with concurrent diagnosis of primary melanoma with nodal involvement, major surgical procedure other than lymph node biopsy or wide local excision of primary melanoma  $\leq 4$  weeks prior to pre-registration, or anticipation of need for a major surgical procedure for reasons other than melanoma during the course of the study.

3.24 For patients with nodal recurrence, surgical procedure or anti-cancer therapy for this recurrence (other than lymph node biopsy) or anticipation of need for a major surgical procedure for reasons other than melanoma during the course of the study.

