#### **All institutions**

- 6.23 IRB approvals
- Documentation of IRB approval must be on file in the Research Site Management Office before an investigator may register any patients.
- In addition to submitting initial IRB approval documents, ongoing IRB approval documentation must be on file (no less than annually) at the Research Site Management Office [REDACTED]. If the necessary documentation is not submitted in advance of attempting patient registration, the registration will not be accepted and the patient may not be enrolled in the protocol until the situation is resolved.
- When the study has been permanently closed to patient enrollment, submission of annual IRB approvals to the Research Site Management Office is no longer necessary.
- 6.24 Verification
- At the time of registration, the Research Registration Application will verify the following:
- IRB approval
  - Patient eligibility
- 6.25 Pretreatment tests/procedures (see Section 4.0) must be completed within the guidelines specified on the test schedule.
- 6.26 Consent and treatment on this protocol must commence at Mayo Clinic Rochester or a participating site under the supervision of a medical oncologist.
- 6.27 Treatment cannot begin prior to registration and must begin  $\leq 14$  days after registration.
- 6.28 All required baseline symptoms (see Section 10.6) must be documented and graded.
- 6.29 Blood draw/biospecimen kits must be available on site for patients being treated outside of Mayo Clinic in Rochester, MN.

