## 10.6 Required Routine Reporting

### 10.61 Baseline and Adverse Events Evaluations

Pretreatment symptoms/conditions to be graded at baseline and adverse events to be graded at each evaluation.

Grading is per CTCAE v4.0 **unless** alternate grading is indicated in the table below:

CTCAE System Organ Class (SOC)	Adverse event/Symptoms	Baseline	Each evaluation
Blood and lymphatic system disorders	Anemia	X	X
Gastrointestinal disorders	Baseline # stools	X	
	Diarrhea		X
General disorders	Fatigue	X	X
	Fever		X
Immune system disorders	Allergic reaction		X
	Anaphylaxis		X
Investigations	Blood bilirubin increased	X	X
Respiratory, thoracic and mediastinal disorders	Dyspnea	X	X
Skin and subcutaneous tissue disorders	Rash, acneiform	X	X
	Rash, maculo-papular	X	X

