#### **c. Preexisting Medical Conditions**

A preexisting medical condition is one that is present at the start of the study. Such conditions should be reported as medical and surgical history. A preexisting medical condition should be re-assessed throughout the trial and reported as an AE or SAE only if the frequency, severity, or character of the condition worsens during the study. When reporting such events, it is important to convey the concept that the preexisting condition has changed by including applicable descriptors (e.g., “more frequent headaches”).

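### Lymphedema has no graded baseline, so new or worsened cases cannot be reliably told from pre-existing ones

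*Combined protocol and SAP*

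**What the plan says.** The Arm C schedule (Section 4.2) has a row headed "Evaluation of kymphedema using NCI CTCAE v5.0" (the spelling is the document's), marked only under adjuvant treatment and observation. Its footnote 30 reads: "At completion of adjuvant treatment and 12 months post surgery only; Please put results on Adverse Event: Other CRF". Footnote 3 in Section 4.1 sets the same rule for Arms A and B. Neither schedule marks this row before registration, before surgery or at the visit just before adjuvant treatment.

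Section 6.28 sets the baseline duty: "All required baseline symptoms (see Section 10.6) must be documented and graded". Section 10.61 supplies the list, introduced as "Pretreatment symptoms/conditions to be graded at baseline and adverse events to be graded at each evaluation". The baseline entries are anemia, number of stools, fatigue, bilirubin, dyspnea and two kinds of rash. Lymphedema is not among them.

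Section 10.83c covers conditions present at study start. "Such conditions should be reported as medical and surgical history", it says, and they are "reported as an AE or SAE only if the frequency, severity, or character of the condition worsens during the study".

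Section 3.12 admits recurrent nodal metastasis as one form of high-risk disease. Section 3.24 excludes surgery for the present recurrence other than node biopsy. It does not exclude an earlier nodal operation.

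**The concern.** Some patients may enter with lymphedema from earlier nodal surgery. Their first dedicated grade comes after a further node dissection and after adjuvant treatment, and it goes on an adverse event form. Deciding whether that grade is new, worse or unchanged needs a starting grade, and the plan does not require one.

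Two things are at stake. Objectives 2.21 to 2.23 ask for adverse event frequencies across neoadjuvant treatment, surgery and adjuvant treatment, and lymphedema contributes to those counts. Section 1.4 also cites lymphedema as a long-term morbidity of dissecting high-volume nodal disease, as part of the case for neoadjuvant therapy, so readers will look for an interpretable figure.

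A second issue is timing. The first reading is tied to the end of adjuvant treatment, so patients may be read at different times since surgery.

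**Working it through.** The plan gives no rate, interval or sample size for lymphedema, so there is no figure to reproduce. The check is textual, with simple arithmetic on timing and on the weight of one case.

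**Can the worsening rule be applied?**
- Rule (10.83c): an unworsened pre-existing condition is history, not an adverse event.
- Needed: a grade before treatment or surgery, and a later grade on the same scale.
- Available before treatment: history and exam at pre-registration and a general adverse event assessment within 14 days before registration (4.2). Neither requires a lymphedema grade, because the list in 10.61 omits it.
- Available later: a CTCAE v5.0 grade at the two footnoted times. Section 10.61 defaults to v4.0, so an incidental early grade may be on another version.
- Result: worsening can be judged only where a site happens to have recorded enough detail.

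**What do the general assessments capture?** They run after each neoadjuvant cycle, within 7 days before adjuvant treatment, after each adjuvant cycle and in observation. Section 10.62 requires routine reporting of related Grade 2 and all Grade 3 and 4 events. Grade 1 and unrelated Grade 2 lymphedema have no required route before the dedicated evaluation, which has no grade floor.

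**When does the first dedicated reading fall?**
- Inputs: a cycle is 21 ±3 days, with at most 8 cycles (7.3). Patients may stop early for toxicity or refusal and go to observation (13.32). The gap from surgery to adjuvant start is not stated; 0 to 6 weeks is assumed.
- Formula: weeks after surgery = gap + 3 × cycles given, with no dose holds.
- 1 cycle: 0 + 3 = 3 to 6 + 3 = 9 weeks.
- 4 cycles: 0 + 12 = 12 to 6 + 12 = 18 weeks.
- 8 cycles: 0 + 24 = 24 to 6 + 24 = 30 weeks. If every cycle runs 3 days short or long, this becomes 8 × 18/7 = 20.6 to 6 + 8 × 24/7 = 33.4 weeks.
- Overall: about week 3 to week 30, if stopping early counts as completion. If completion means all 8 cycles, as Section 13.34 may suggest, the spread is about 24 to 30 weeks and early stoppers have only the 12-month reading.

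**How much does one case weigh?**
- Arm C has 32 patients starting treatment (16.1112): 1/32 = 3.1 points. Arms A and B have 15 each: 1/15 = 6.7 points. Fewer patients assessed would mean a larger step.
- Illustration with assumed counts: 4 new cases give 4/32 = 12.5% (exact 90% interval 4.4 to 26.4%). Counting 3 pre-existing cases as new gives 7/32 = 21.9% (10.7 to 37.2%).

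**The case against.** The strongest reply is that the plan already handles pre-existing conditions. Section 10.83c sends them to medical history and allows an adverse event report only on worsening; the footnotes name a form and do not suspend that rule. General assessments run throughout, and related Grade 2 and all Grade 3-4 events are reportable. The 12-month reading is at a fixed time after surgery. Lymphedema is named in no objective and in no part of Section 16. With no surgery-first control, even a good baseline could not show that neoadjuvant therapy reduces it.

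Most of this stands, and it rules out three stronger readings.
- A reader might infer that pre-existing lymphedema is counted as an on-study event. No section says so, and 10.83c says the opposite for unworsened conditions.
- A reader might infer that lymphedema goes wholly unrecorded in the neoadjuvant and early post-operative periods. What is missing is a scheduled lymphedema evaluation; the general reporting route exists.
- A reader might want to state how many of the 32 are affected. The documents give no prevalence, and recurrent nodal disease does not by itself establish an earlier dissection, still less lymphedema.

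The reply does not remove the gap. Section 10.83c depends on a comparison for which no starting grade is required, and a history entry need not carry one.

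**Conclusion.** The point holds as a limited weakness in descriptive safety data. Because no baseline grade is required, new or worsened lymphedema cannot be reliably separated from pre-existing lymphedema, as the plan's own rule needs.

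The size is bounded but not known: 3.1 points on a crude Arm C rate per misclassified case, with the number of such cases unknown. The 3-to-30-week spread rests on the assumed 0-to-6-week gap, on no dose holds, and on reading completion to include early stopping. It affects the first reading only, not the 12-month one. pCR, RFS and sample size are untouched.

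**What to change.** For patients still to enroll in Arm C:
- Add a lymphedema grade, stated as CTCAE v5.0, to the pre-registration history and exam, to the baseline list in Section 10.61, and to the exam at or under 7 days before adjuvant treatment. Naming the version matters because 10.61 otherwise defaults to v4.0.
- Report new or worsened lymphedema relative to baseline, with 12 months post surgery as the main time point.

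For Arms A and B, which are closed to enrollment, and for Arm C patients already treated, report the missing baseline as a limitation.

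The cost is one added CRF field at two visits that already exist. It cannot recover a baseline for patients already treated.
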